6.2.1.4. Hypoglycemia

Any hypoglycemic AEs will be listed in a separate table and summarized categorically by treatment as per [Section 5.2.2](#).

6.2.1.5. Laboratory Data

Laboratory data will be listed and summarized by treatment in accordance with the sponsor reporting standards. Baseline is as defined in [Section 3](#).

6.2.1.6. Vital Signs Data

Average of the triplicate measurements (where applicable) will be used in analyses.

Unless specified otherwise, for non-maximum summaries unplanned assessments will not be considered.

Absolute values and changes from baseline in supine systolic and diastolic blood pressure and pulse rate will be summarized by treatment group and time point, according to sponsor reporting standards. Tables will be paged by parameter.

Baseline is as defined in [Section 3](#).

Mean changes from baseline for systolic and diastolic blood pressure and pulse rate will be plotted against time point. On each plot there will be 1 line for each treatment group with all treatments on the same plot.

For baseline subtracted supine systolic and diastolic blood pressure and pulse rate, the differences between each treatment group of PF-07081532 and placebo (treatment – placebo, using the placebo from the respective population) will be summarized (N, mean, 90% CI) and plotted (mean, 90% CI) for each treatment group of PF-07081532 and time point.

Participants with absolute values and changes from baseline for vital signs (over all post-dose measurements) meeting categories as defined in the [Appendix 2](#) will also be summarized descriptively by treatment group. Numbers and percentages of participants meeting the categorical criteria will be provided. All planned and unplanned post-dose time points will be counted in these categorical summaries. All values meeting the criteria of potential clinical concern will be listed.

Maximum decrease and increase from baseline for supine systolic and diastolic blood pressures, and maximum increase from baseline for supine pulse rate will be summarized by treatment group, according to sponsor reporting standards.

Data from all cohorts will be plotted on the same figure using a single line for the placebo group(s). Corresponding individual plots of change from time-matched baseline will also be produced for each treatment.

The time-matched double differences in vital signs obtained following the Day 1 treatment, as defined in [Section 3](#), will be summarized (N, mean, 90% confidence interval) for each treatment and time point. In addition, the time-matched double differences between each treatment and placebo will be summarized (N, mean, 90% confidence interval) for each treatment, time post-dose and day.

Mean time-matched double differences in vital signs will be plotted against time post-dose for each Day as defined in the SoA separately. On each plot there will be 1 line for each treatment and a single line for the placebo group(s). Corresponding individual plots of time-matched double differences will also be produced for each treatment. The mean plots will similarly be produced for the time-matched double differences between each treatment and placebo.

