### 2.3. Benefit/Risk Assessment

This study is designed primarily to generate safety, tolerability, and PK data from adult participants with T2DM and, potentially, participants with obesity and without T2DM. The purpose of the study is to provide the basis for further clinical development of PF-07081532 as a potential new, pharmacological agent for the treatment of T2DM.

Based on the clinical history of injectable GLP-1R agonists, an oral GLP-1R agonist is expected to improve glucose control, reduce HbA1c levels, diminish food intake, and decrease body weight in patients with T2DM, while avoiding the requirement for subcutaneous injections that accompany a majority of currently available peptidic GLP-1R agonists.

As of the issuance of this protocol, no specific human risks associated with PF-07081532 administration have been identified. The doses being evaluated in this study are anticipated to be in the range of doses previously tested. Data gathered during nonclinical and clinical studies with PF-07081532 to date are summarized in the current IB and in [Section 2.2](#).

Potential Risk of Clinical Significance	Summary of Data/Rationale for Risk	Mitigation Strategy
Study Intervention – PF-07081532		
Potential risks associated with marketed GLP-1R agonists including thyroid C-Cell tumors, pancreatitis, changes in heart rate and blood pressure	The potential risks are based on product labeling for marketed GLP-1R agonists (liraglutide, dulaglutide, and exenatide); additional information is provided in the current IB.	
 
• Study includes inpatient monitoring of the participants following administration of multiple, oral doses of the investigational product.
 
• Potential participants with a personal or family history of medullary thyroid carcinoma or MEN2 are not eligible for study entry. Potential participants with acute pancreatitis or a history of chronic pancreatitis are not eligible for study entry.
 
• Clinical safety laboratory tests, including thyroid function, serum amylase and lipase, thorough assessments of vital signs and ECGs, physical examinations and adverse event monitoring will be undertaken throughout the dosing period.
 

Gastrointestinal adverse events	The potential risks are based on product labeling for marketed GLP-1R agonists (liraglutide, exenatide and	Participants are monitored during the study to prevent potential sequelae of any severe gastrointestinal reactions,

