### **Diagnostic Assessments:**

14. A positive urine drug screen at screening or admission.

**Note:** Participants who have been medically prescribed benzodiazepines and report the use of these drugs to the investigator at the screening visit may be allowed to participate if approved by the sponsor.

15. Positive testing at screening for HIV, HBsAg, HBcAb, HBsAb or HCVAb. Positive COVID-19 test at screening or admission.

**Note:** A positive HBsAb due to hepatitis B vaccination is permissible.

16. Screening supine BP  $\geq 160$  mm Hg (systolic) or  $\geq 100$  mm Hg (diastolic) following at least 5 minutes of supine rest.

If BP is  $\geq 160$  mm Hg (systolic) or  $\geq 100$  mm Hg (diastolic), the BP should be repeated 2 more times and the average of the 3 BP values should be used to determine the participant's eligibility.

17. Screening 12-lead ECG that demonstrates clinically relevant abnormalities that may affect participant safety or interpretation of study results (eg, baseline QTcF interval  $>450$  msec, complete LBBB, signs of an acute or indeterminate-age myocardial infarction, ST-T interval changes suggestive of myocardial ischemia, second- or third-degree AV block, or serious bradyarrhythmias or tachyarrhythmias).

If QTcF exceeds 450 msec, or QRS exceeds 120 msec, the ECG should be repeated 2 more times and the average of the 3 QTcF or QRS values should be used to determine the participant's eligibility. Computer-interpreted ECGs should be overread by a physician experienced in reading ECGs before excluding participants.

18. Participants with **ANY** of the following abnormalities in clinical laboratory tests at screening, as assessed by the study-specific laboratory and confirmed by a single repeat test if deemed necessary:

- AST or ALT level  $\geq 1.5$  times ULN;

- Total bilirubin level  $\geq 1.5$  times the ULN; participants with a history of Gilbert's syndrome may have direct bilirubin measured and would be eligible for this study provided the direct bilirubin level is  $\leq$  ULN;
- TSH > ULN;
- Fasting C-peptide <0.8 ng/mL;
- Serum calcitonin > ULN;
- Amylase > ULN;
- Lipase > ULN;
- eGFR <60 mL/min/1.73m^2 as calculated by MDRD equation;
- FPG >270 mg/dL at **screening or admission**.

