#### 9.3.1. General Considerations

#### 9.3.2. Primary Endpoint

All participants who received at least 1 dose of study intervention will be included in the safety analyses and listings. AEs, ECGs, BP, pulse rate, and safety laboratory data will be reviewed and summarized on an ongoing basis during the study to evaluate the safety of

participants. Any clinical laboratory, ECG, BP, and pulse rate abnormalities of potential clinical concern will be described. Safety data will be presented in tabular and/or graphical format and summarized descriptively, where appropriate.

Medical history and physical examination information, as applicable, collected during the course of the study will be considered source data and will not be required to be reported, unless otherwise noted. However, any untoward findings identified on physical and/or neurological examinations conducted during the active collection period will be captured as AEs, if those findings meet the definition of an AE.

Data collected at screening that are used for inclusion/exclusion criteria, such as laboratory data (unless noted below), ECGs, and vital signs, will be considered source data, and will not be required to be reported, unless otherwise noted. Demographic data collected at screening will be reported. In addition, selected screening laboratory data: free T4, HbA1c, TSH, calcitonin, amylase, lipase, TBA and C-peptide will be reported.

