Appendix 2. Categorical Classes for ECG and Vital Signs of Potential Clinical Concern

Categories for QTcF

Absolute value of QTcF (msec)	>450 and ≤480	>480 and ≤500	>500
Increase from baseline in QTcF (msec)	>30 and ≤60	>60	

Categories for PR and QRS

PR (ms)	max. ≥300	
PR (ms) increase from baseline	Baseline >200 and max. ≥25% increase	Baseline ≤200 and max. ≥50% increase
QRS (ms)	max. ≥140	
QRS (ms) increase from baseline	≥50% increase	

Categories for Vital Signs

Systolic BP (mm Hg)	min. <90	
Systolic BP (mm Hg) change from baseline	max. decrease ≥30	max. increase ≥30
Diastolic BP (mm Hg)	min. <50	
Diastolic BP (mm Hg) change from baseline	max. decrease ≥20	max. increase ≥20
Supine pulse rate (bpm)	min. <40	max. >120

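### SAP Appendix 2 flags high blood pressure only as a rise from baseline, so a participant with a high baseline can pass the trial's own entry limit unflagged

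*SAP*

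**What the plan says.** SAP 6.2.1.6 summarises, by treatment group, participants with "Participants with absolute values and changes from baseline for vital signs (over all post-dose measurements) meeting categories as defined in the" Appendix 2. Planned and unplanned post-dose readings both count. It adds: "All values meeting the criteria of potential clinical concern will be listed".

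The vital-signs part of Appendix 2 contains:

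- **Systolic:** an absolute minimum below 90; a fall of at least 30; a rise, "max. increase ≥30".
- **Diastolic:** an absolute minimum below 50; a fall of at least 20; a rise, "max. increase ≥20".
- **Supine pulse:** a minimum below 40 and a maximum above 120.

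SAP 3.1.3 takes the Day -1 triplicate average as baseline.

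In the protocol, exclusion criterion 16 (section 5.2) removes people whose screening pressure is at or above 160 systolic or 100 "mm Hg (diastolic) following at least 5 minutes of supine rest". Exclusion 1 lets in controlled chronic conditions such as hypertension. The benefit/risk table in section 2.3 names "Potential risks associated with marketed GLP-1R agonists including thyroid C-Cell tumors, pancreatitis, changes in heart rate and blood pressure". Section 9.3.2, on the primary endpoint, says that "BP, and pulse rate abnormalities of potential clinical concern will be described".

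**The concern.** Vital signs are part of the primary endpoint, and blood pressure change is a named potential risk with no direction attached. The absolute categories for blood pressure nevertheless look only downwards. On the high side everything depends on the change from baseline, and that criterion is least sensitive to a high absolute level in the participants who start highest.

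The ECG section shows the contrast. SAP 6.2.1.7 summarises each participant's maximum absolute post-dose QTcF, PR and QRS, whereas SAP 6.2.1.6 summarises only the maximum changes in blood pressure. No planned blood pressure table counts participants above a stated level.

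What is at stake is how the outlier table will be read. It could show no high blood pressure value of potential clinical concern while some participants had readings above the level that would have kept them out of the trial. With about 9 active and 3 placebo participants per cohort, individual outliers carry much of the safety information, so the table should look in both directions.

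**Working it through.** The plan states no figure on this point, so there is none to reproduce. The check applies the Appendix 2 rules to possible baselines.

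**Inputs**

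- Absolute flags: systolic <90, diastolic <50 (SAP Appendix 2).
- Upward change flags: systolic rise ≥30, diastolic rise ≥20 (SAP Appendix 2).
- Highest screening pressure that is eligible, in whole mm Hg: 159/99 (Protocol exclusion 16).
- Baseline: Day -1 (SAP 3.1.3).

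**Rule.** In whole mm Hg, a high reading escapes every category when the systolic rise is at most 29 and the diastolic rise is at most 19. So:

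highest unflagged systolic = baseline + 29; highest unflagged diastolic = baseline + 19.

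| Baseline | Highest unflagged reading |
|---|---|
| 120/75 | 149/94 |
| 130/80 | 159/99 |
| 140/85 | 169/104 |
| 150/90 | 179/109 |
| 159/99 | 188/118 |

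**The same rule in reverse.** Lowest unflagged baseline = reading − 29 systolic, reading − 19 diastolic.

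| Post-dose reading | Unflagged from this baseline up |
|---|---|
| 160/100 | 131/81 |
| 170/105 | 141/86 |
| 180/110 | 151/91 |
| 188/118 | 159/99 |

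**How extreme is the corner case?** From 158/98, a reading of 188/118 is +30/+20 and meets both rise categories. From 159/98 the diastolic rise is 20 and is flagged; from 158/99 the systolic rise is 30 and is flagged. Among whole-number baselines within the entry limit, 159/99 is the only one that leaves 188/118 wholly unflagged. The 150/90 example is the more useful one.

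**Screening against Day -1.** Exclusion 16 applies to the screening measurement, while change is taken from Day -1. A Day -1 baseline above 159/99 is therefore possible, and the unflagged ceiling would rise with it.

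**After the change.** With upper categories at ≥160 systolic and ≥100 diastolic, 179/109 and 188/118 are both flagged whatever the baseline.

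**The case against.** The strongest reply is that high readings remain visible elsewhere, and this stands:

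- SAP 6.2.1 says the safety endpoints of Section 3.1, which include vital signs, will be listed and summarised. A reading of 188/118 would be in that listing.
- SAP 6.2.1.6 summarises absolute values by treatment and time point, and SAP 5.2.1 includes the maximum among the statistics. The highest planned reading in each arm should print at each time point. Unplanned readings are left out of these summaries.
- The maximum increase from baseline is summarised by treatment group.
- Protocol Appendix 3 makes a vital-sign abnormality an adverse event if the investigator judges it clinically significant.

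A reader might infer that high blood pressure would go unreported. The documents do not support that; the gap is confined to the categorical table and the listing tied to it.

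A second reply is that the rise criterion fits the named risk, which is a change in blood pressure, and keeps pre-existing hypertension from being read as a drug effect. This is a fair reason to keep the rise categories. It does not explain why pulse, named in the same risk entry, has an upper absolute limit and blood pressure has none.

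A reader might also infer that the SAP breaks the commitment in Protocol 9.3.2. It does not: that section sets no blood pressure threshold.

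Finally, exclusion 16 is an eligibility limit and not a post-dose threshold of concern. That is correct, and it is why the cut-off is for the sponsor to choose.

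**Conclusion.** The point holds as a modest gap in the outlier reporting of a primary safety endpoint. A participant with a high baseline can exceed 160/100 and enter neither the categorical table nor the listing of values of potential clinical concern. For a reading of 160/100 this is so from a baseline of 131/81 up; for 180/110, from 151/91 up.

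The conclusion rests on Appendix 2 as written and on whole-number readings. The sponsor reporting standards to which SAP 6.2.1.6 also refers are not in the documents, but that section takes its categories from Appendix 2.

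How often this would happen cannot be stated. The documents give no blood pressure distribution for this population and no expected drug effect on blood pressure, so any percentage would reflect assumed inputs. It is also tempting to conclude that 188/118 typically escapes; it does so only from the 159/99 corner, or from a Day -1 value above the screening limit. The case for the change is that it is specific and cheap and makes the table two-sided, not that a safety signal would otherwise be lost.

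**What to change.** Add pre-specified upper absolute categories for systolic and diastolic pressure to SAP Appendix 2, for reporting only. The exclusion 16 values (maximum ≥160 systolic, maximum ≥100 diastolic) are a ready reference. If the sponsor prefers another cut-off, state it in the SAP before the analysis. Keep the existing rise and fall categories.

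Tabulate the new categories by treatment group with placebo alongside. Include the values in the existing listing, and show each flagged participant's baseline next to the reading. A formal split by baseline level is optional: with about 9 active and 3 placebo participants per cohort its cells would be very small, and the baseline column serves the same purpose.

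The cost is two more rows in a planned table, additional entries in a planned listing, and no new data. The downside is that some readings from participants whose pressure was already high at baseline will be flagged; the baseline column and the placebo group put these in context.

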6.2.1.7. Electrocardiograms Data

Average of the triplicate measurements (where applicable) will be used in analyses.

Unless specified otherwise, for non-maximum summaries unplanned assessments will not be considered.

Absolute values and changes from baseline in QT interval, heart rate, QTcF interval, PR and QRS will be summarized by treatment group and time point using sponsor reporting standards. Tables will be paged by parameter. Baseline is as defined in [Section 3](#).

Mean changes from baseline in QT interval, heart rate and QTcF will be plotted against time point. On each plot there will be 1 line for each treatment group with all treatments included on the same plot.

In addition for baseline subtracted QT, heart rate and QTcF, the differences between each treatment group of PF-07081532 and placebo (treatment – placebo, using the placebo from the respective population) will be summarized (N, mean, 90% CI) and plotted (mean, 90% CI) for each treatment group of PF-07081532 and time point.

Participants with ECG endpoints and changes from baseline (QTcF, PR and QRS) meeting categories as defined in the [Appendix 2](#) (for QTcF these correspond to the Pfizer Guidance [2]) will also be summarized descriptively by treatment group. Numbers and percentages of participants meeting the categorical criteria will be provided. All planned and unplanned post-dose time points will be counted in these categorical summaries. All values meeting the criteria of potential clinical concern will be listed.

Maximum absolute value (post-dose) and the maximum increase from baseline for QTcF, PR and QRS will be summarized by treatment group according to sponsor reporting standards.

Listings of participants with any single post-dose value > 500 msec will also be produced for QTcF.

Mean change from time-matched baseline in ECG parameters will be plotted against day. On each plot there will be 1 line for each treatment and a single line for the placebo group(s). Corresponding individual plots of change from time-matched baseline will also be produced for each treatment.

The time-matched double differences in QT, QTcF, PR, QRS intervals and heart rate measures obtained following the Day 1 treatment, as defined in [Section 3.1](#), will be summarized (N, mean, 90% confidence interval) for each treatment and time point. In addition, the differences between each treatment and placebo will be summarized (N, mean, 90% confidence interval) for each treatment, time postdose and day.

Mean time-matched double differences in ECG parameters will be plotted against time postdose for each Days as defined in the SoA separately. On each plot there will be 1 line for each treatment and a single line for the placebo group(s). Corresponding individual plots of time-matched double differences will also be produced for each treatment. The mean plots will similarly be produced for the time-matched double differences between each treatment and placebo.

The time-matched double differences in QTcF will be plotted against PF-07081532 concentration. This will be a scatter plot for all observations where QTcF and drug concentration are recorded. Placebo data will also be included (with drug concentration set to zero). Different symbols will be used for each treatment.

6.3. Secondary Endpoint(s)

6.3.1. PF-07081532 PK Parameters

- Estimand strategy: Not applicable
- Analysis set: PF-07081532 Concentration and Pharmacokinetic Parameter Set

To assess the pharmacokinetics of PF-07081532, the PK parameters detailed in [Section 3.2](#) will be listed and summarized for participants in the PK analysis set (as defined in [Section 4](#)). Missing values will be handled as detailed in [Section 5.3](#) along with handling of values where participants received a dose that was not assigned based on the titration scheme). Each PK parameter will be summarized by treatment (eg differentiating different doses and dosing frequencies as required), and Study Day (Day 1, and 42, as applicable).

The parameters will include the set of summary statistics as specified in the table below:

Table 3. PF-07081532 PK Parameters to be Summarized Descriptively

Parameter	Matrix	Summary Statistics
AUC ₂₄ , AUC ₂₄ (dn), C _{max} , C _{max} (dn), PTR, R _{ac} , C _{av} , C _{min} , R _{ac,Cmax} , , CL/F, Vz/F, AUC _{inf} , AUC _{last}	Plasma	N, arithmetic mean, median, cv%, standard deviation, minimum, maximum, geometric mean and geometric cv%.
T _{max}	Plasma	N, median, minimum, maximum.

$t_{1/2}$	Plasma	N, arithmetic mean, median, cv%, standard deviation, minimum, maximum.
-----------	--------	--

There will be one summary table presenting all PK parameters. The treatment subheading will include the analyte, matrix, dose information and day (Day 1, or Day 42). As per [Section 5.3.3](#), data collected on days that participants received anything other than the assigned dose based on the titration scheme will only be listed and not summarized as part of the summary table.

To assess the relationship between the PK parameters and dose for PF-07081532, dose normalized AUC_{24} and C_{max} will be plotted against treatment (using a logarithmic scale) for Day 1, and Day 42 separately and will include individual participant values and the geometric means for each dose. Geometric means will have a different symbol than the individual values. The values will be dose normalized (to a 1 mg dose) by dividing the individual values and raw geometric means by dose. A footnote will be added to the plots to indicate that geometric means are presented.

The observed accumulation ratio for AUC_{24} and C_{max} will be analyzed after natural log transformation using a one-way analysis of variance with a single term for dose. The means and 90% confidence intervals (CIs) obtained from the model will be back-transformed to provide means and 90% CIs for the accumulation for each dose.

Supporting data from the estimation of $t_{1/2}$ will be listed where applicable: terminal phase rate constant (k_{el}); goodness of fit statistic from the log-linear regression (r^2); and the first, last, and number of time points used in the estimation of k_{el} . This data may be included in the clinical study report.

Presentations for PF-07081532 concentrations will include:

- a listing of all concentrations sorted by participant ID, treatment, day and nominal time postdose. The concentration listing will also include the actual times. Deviations from the nominal time will be given in a separate listing.
- a summary of concentrations by treatment, day and nominal time postdose, where the set of statistics will include n, mean, median, standard deviation, coefficient of variation (cv), minimum, maximum and the number of concentrations above the lower limit of quantification.
- median concentrations time plots (on both linear and semi-log scales) against nominal time postdose by treatment (all treatments on the same plot per scale, based on the summary of concentrations by treatment and time postdose), for Day 1 and Day 42 .
- mean concentrations time plots (on both linear and semi-log scales) against nominal time postdose by treatment (all treatments on the same plot per scale, based on the summary of concentrations by treatment and time postdose), for Day 1 and Day 42.

- individual concentration time plots by treatment (on both linear and semi-log scales) against actual time postdose (there will be separate spaghetti plots for each treatment per scale), paged by day (and also equivalent plots spanning the entire study duration – not paged by day).
- Median trough concentrations time plots (on both linear and semi-log scales) against nominal time post dose by treatment, spanning the entire study duration, i.e. not paged by day (all treatments on the same plot per scale, based on the summary of concentrations by treatment and time postdose)

The length of time used for the x-axes of these plots will be decided on review of the data, and will depend on how long PF-07081532 concentration is quantifiable in the matrix.

For summary statistics, median and mean plots by sampling time, the nominal PK sampling time will be used; for individual participant plots by time, the actual PK sampling time will be used.

